8.1 Subject Inclusion Criteria

Subject eligibility should be reviewed and documented by an appropriate member of the investigator's study team before subjects are included in the study.

Subjects must meet all of the following inclusion criteria to be eligible for enrollment in to the study:

1. Subjects must be of legal age (at least 18 years) on the date the Informed Consent Form (ICF) is signed.
2. Subjects must be able to read, understand, and provide written informed consent on the Institutional Review Board (IRB)/Ethics Committee (EC)-approved ICF and provide authorization as appropriate for local privacy regulations.
3. Subjects who are willing and able to comply with scheduled visits, treatment plan, and other study procedures.
4. Male subjects able to father children and female subjects of childbearing potential and at risk for pregnancy must agree to use a highly effective method of contraception throughout the study and for at least 28 days after last dose of assigned treatment.

Acceptable contraceptive methods for female subjects (need at least one):

- a) Hormonal methods of contraception (including oral and transdermal contraceptives, injectable progesterone, progestin subdermal implants, progesterone-releasing intrauterine devices [IUDs]) initiated at least 14 days prior to the first dose of study drug
- b) True abstinence: when this is in line with the preferred and usual lifestyle of the subject. Periodic abstinence (eg, calendar, ovulation, symptothermal, post-ovulation methods) and withdrawal are not acceptable methods of contraception
- c) Placement of a copper-containing IUD
- d) Condom with spermicidal foam/gel/film/cream/suppository

- e) Postmenopausal at least 12 months (365 days) prior to the first dose of study drug or permanently sterilized (eg, tubal occlusion, hysterectomy, bilateral salpingectomy)
- f) Male partner who has had a vasectomy for at least 3 months (90 days) prior to the first dose of study drug or is surgically sterile

Acceptable contraceptive methods for male subjects with partners of childbearing potential (need at least one):

- a) True abstinence: when this is in line with the preferred and usual lifestyle of the subject. Periodic abstinence (eg, calendar, ovulation, symptothermal, post-ovulation methods) and withdrawal are not acceptable methods of contraception.
- b) Vasectomy for at least 3 months (90 days) prior to the first dose of study drug or surgically sterile
- c) Without a vasectomy, must use a condom with spermicidal foam/gel/film/cream/suppository

5. Female subjects who are not of childbearing potential must meet at least 1 of the following criteria:

- a. Have undergone a documented hysterectomy and/or bilateral oophorectomy, and/or tubal ligation;
- b. Have medically confirmed ovarian failure; or
- c. Achieved postmenopausal status, defined as follows: cessation of regular menses for at least 12 consecutive months with no alternative pathological or physiological cause

6. Diagnosis of primary-open angle glaucoma (including pigmentary or pseudoexfoliative) or ocular hypertension and requires treatment in both eyes.

7. Adequate wash-out period prior to baseline of any ocular hypotensive medication (see Table 1). In order to minimize potential risk to patients due to intraocular pressure (IOP) elevations during the washout period, the investigator may choose to substitute a parasymphomimetic or carbonic anhydrase inhibitor in place of a

sympathomimetic, alpha-agonist, beta-adrenergic blocking agent, or prostaglandin; however, all patients must have discontinued all ocular hypotensive medication for the minimum washout period provided in Table 1.

8. Baseline (Day 1/hour 0) IOP ≥ 22 mmHg and ≤ 34 mmHg in both eyes and ≤ 5 mmHg IOP difference between eyes.
9. Screening and Baseline/Visit 1 BCVA equivalent to 20/200 or better in each eye.
10. Negative urine pregnancy test at screening and baseline for women of childbearing potential.

8.2 Subject Exclusion Criteria

Subjects with any of the following characteristics/conditions will not be included in the study:

1. Subjects who are investigational site staff members directly involved in the conduct of the study and their family members, site staff members otherwise supervised by the investigator, subjects who are Sponsor employees directly involved in the conduct of the study, or household members of current subjects in the study.
2. Subjects participating in any clinical investigation within 30 days prior to Screening.
3. Any severe, acute, or chronic medical or psychiatric condition that may increase the risk associated with the study participation or investigational product administration or could interfere with the interpretation of study results and, in the judgment of the investigator, could make the patient inappropriate for entry in to this study.
4. Pregnant female subjects; breastfeeding female subjects; male subjects with partners currently pregnant; male subjects able to father children and female subject of childbearing potential who are unwilling or unable to use highly effective method of contraception as outlined in this protocol for the duration of the study and for at least 28 days after the last dose of investigational product.
5. Current or past history of severe hepatic or renal impairment.

6. Current or history within two months prior to baseline of significant ocular disease (eg, macular degeneration, hypertensive retinopathy, diabetic retinopathy, corneal edema, uveitis, ocular infection, or ocular trauma in either eye) that may increase the risk associated with the study participation or investigational product administration or could interfere with the interpretation of study results and, in the judgment of the investigator, could make the patient inappropriate for entry in to this study.
7. Current corneal abnormalities or any condition that would prevent accurate IOP readings with the Goldmann applanation tonometer.
8. Functionally significant visual field loss in either eye, measured within 6 months prior to screening.
9. At the screening visit, advanced glaucoma defined by both a horizontal and vertical cup/disc ratio >0.8 in either eye.
10. Contraindication to brinzolamide or sulfonamide therapy or known hypersensitivity to any component of brinzolamide or sulfonamide therapy.
11. Use at any time prior to baseline of an intraocular corticosteroid implant.
12. Use within one week prior to baseline of contact lenses.
13. Use within two weeks prior to baseline of: 1) topical ophthalmic corticosteroid; 2) topical corticosteroid; 3) systemic corticosteroid, or 4) high dose salicylate therapy (defined as stable daily doses exceeding 325 mg aspirin or equivalent)
14. Use within six months prior to baseline intravitreal or subtenon injection of ophthalmic corticosteroid.
15. Intraocular or refractive surgery (eg, cataract surgery, LASIK, etc.) within six months prior to Screening.
16. IOP lowering surgery (eg, Trabeculectomy, Laser trabeculoplasty, tube shunts, etc.) within 12 months prior to baseline.
17. History of severe dry eye in either eye.
18. Persons with Central Corneal Thickness (CCT) $>600\mu\text{m}$ in either eye.

19. Anticipate the need to initiate or modify medication (systemic or topical) that is known to affect IOP or blood pressure (eg, β -adrenergic antagonists, α -adrenergic agonists, calcium channel blockers, angiotensin-converting enzyme (ACE) inhibitors, and angiotensin II receptor blockers) during the study period.
20. Subjects with very narrow angles (3 quadrants with less than Grade 2 according to Shaffer's anterior chamber angle grading system) and subjects with angle closure, congenital, and secondary glaucoma, and subjects with history of angle closure in either eye.
21. Subjects with known or suspected drug or alcohol abuse.

8.3 Subject Withdrawal Criteria

Withdrawal of consent: Subjects who wish to discontinue study treatment will remain in the study and must continue to be followed for protocol specified follow-up procedures. The only exception to this is when the subject specifically withdraws consent for any further contact with him or her or any persons previously authorized by the subject to provide information. Subjects are completely free to refuse to enter the study or to withdraw at any time, without giving a reason. The withdrawal of consent should be explained in detail in the medical records of the investigator, as to whether the withdrawal is only from further treatment of investigational product or also from study procedures and/or post treatment study follow-up, and entered on the appropriate CRF page. In the event that vital status (whether the subject is alive or dead) is being measured, publicly available information should be used to determine vital status only as appropriately directed in accordance with local law.

For subjects that are lost to follow-up, all reasonable efforts must be made to locate subjects to determine and report their ongoing status. This includes follow-up with persons authorized by the subject as noted above. Prior to discontinuing a subject, every effort should be made to contact the subject, schedule a final study visit, obtain as much follow-up data as possible, and to retrieve all study materials. All attempts should be documented in the subject's medical records. If it is determined that the subject has died, the site will use permissible

local methods to obtain the date and cause of death. If the investigator's use of a third-party representative to assist in the follow-up portion of the study has been included in the subject's informed consent, then the investigator may use a sponsor-retained third-party representative to assist site staff with obtaining the subject's contact information or other public vital status data necessary to complete the follow-up portion of the study. The site staff and representative will consult publicly available sources, such as public health registries and databases, in order to obtain updated contact information. If, after all attempts, the subject remains lost to follow-up, then the last-known-alive date as determined by the investigator should be reported and documented in the subject's medical records.

Subjects may withdraw from the study at any time at their own request, or they may be withdrawn at any time at the discretion of the investigator or sponsor for safety or behavioral reasons, or the inability of the subject to comply with the protocol required schedule of study visits or procedures at a given study site.

Subjects whose condition worsens (eg, IOP \geq 36 mmHg in either eye) and require alternate or supplemental therapy for the treatment of their primary open angle glaucoma or ocular hypertension during the study should be discontinued from the study, excluded from the per-protocol population analysis, and provided with effective treatment.

If a subject does not return for a scheduled visit, every effort should be made to contact the subject. All attempts to contact the subject and information received during contact attempts must be documented in the subject's medical record. In any circumstance, every effort should be made to document subject outcome, if possible. The investigator should inquire about the reason for withdrawal, request that the subject return all unused investigational product(s), request that the subject return for a final visit, if applicable, and follow up with the subject regarding any unresolved AEs. Where possible, the same assessments as Day 42 ([Section \(11.1.5\)](#)), should be completed if the subject withdraws from the study early. If the subject withdraws from the study, and also withdraws consent for disclosure of future information, no further evaluations should be performed, and no additional data should be collected. The sponsor may retain and continue to use any data collected before such withdrawal of consent.

Confidential

9 Treatment Plan

9.1 Study Treatments

For the purpose of this study, and per International Conference on harmonization (ICH) guidelines investigational product is defined as a pharmaceutical form of an active ingredient or placebo being tested or used as a reference in a clinical trial, including a product with a marketing authorization when used or assembled (formulated or packaged) in a way different from the approved form, or when used to gain further information about an approved use (ICH E6 1.33).

9.1.1 Methods of Assigning Subjects to Treatment Groups

Subjects who meet all inclusive/exclusive criteria will be randomized to receive the generic brinzolamide 1% suspension or brinzolamide 1% suspension (AZOPT®) using computer generated, block treatment assignments in a 1:1 ratio stratified by investigational site.

Arm 1: One eye drop of the generic brinzolamide 1% ophthalmic suspension in each eye at approximately 8:00 AM, 4:00 PM and 10:00 PM Daily

Arm 2: One eye drop of brinzolamide 1% ophthalmic suspension (AZOPT®) in each eye at approximately 8:00 AM, 4:00 PM and 10:00 PM Daily

Allocation of subjects to treatment groups will proceed through the use of a randomization and supply management system (Oracle Randomization and Supply Management System [ORS]) (interactive Web-based response [IWR]). The site personnel (study coordinator or specified designee) will be required to enter or select information including but not limited to the user's identification (ID) and password, the protocol number, the subject number and the date of birth of the subject. The site personnel will then be provided with a treatment assignment and Kit Number or container number when drug is being supplied via the ORS system. The ORS system will provide a confirmation report containing the subject number or container number assigned. The confirmation report must be stored in the site files.

There is a 24-hour-a-day, 365-days-a-year ORS helpdesk available for any questions or issues. The study specified ORS reference manual will provide the contact information and further details on the use of the ORS system.

Note: The ORS is the source of the subject number. The ORS system will provide the subject number at the end of the first ORS subject transaction.

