20. Subjects with very narrow angles (3 quadrants with less than Grade 2 according to Shaffer's anterior chamber angle grading system) and subjects with angle closure, congenital, and secondary glaucoma, and subjects with history of angle closure in either eye.
21. Subjects with known or suspected drug or alcohol abuse.

Investigational product, dosage and mode of administration: Subjects who meet all include/exclusion criteria will be randomized to receive the generic brinzolamide 1% suspension or brinzolamide 1% suspension (AZOPT®) using computer generated, blocked treatment assignments in a 1:1 ratio stratified by investigational site.

Arm 1: One eye drop of the generic brinzolamide 1% suspension in each eye at approximately 8:00 AM, 4:00 PM and 10:00 PM Daily

Arm 2: One eye drop of brinzolamide 1% suspension (AZOPT®) in each eye at approximately 8:00 AM, 4:00 PM and 10:00 PM Daily

Confidential

8

Note: the test article must be manufactured compliant to cGMP and meet the proposed ANDA specifications.
Duration of treatment: 42 days (6 weeks) after start of administration of study drug
Reference therapy, dosage and mode of administration: Brinzolamide (AZOPT®) 1% Ophthalmic Suspension
Criteria for evaluation: Efficacy: The primary endpoint is the mean difference in IOP of both eyes between the two treatment groups at four time points, eg, at approximately 8:00 a.m. (hour 0; before the morning drop) and 10:00 a.m. (hour 2) at the Day 14 (week 2) and Day 42 (week 6) visits. Safety: The safety and tolerability of the generic brinzolamide 1% suspension and brinzolamide 1% suspension (AZOPT®) will be evaluated by monitoring of blood pressure and pulse, ophthalmic exams (BCVA, refraction, biomicroscopy, and ophthalmoscopy), and monitoring of treatment related adverse events.

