9.1.2 Treatment Replacement

In the event that a subject's original container is lost, damaged, or consumed prior to the end of treatment, the Investigator will use the ORS, which will specify a new Kit Number to be dispensed to that subject from the supplies already available at the site.

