9.2 Masking

The study subject, investigational staff, investigator, and sponsor personnel will be masked with respect to treatment group. The investigational site will employ procedures to avoid accidental unmasking of the masked staff. A sealed copy of the randomization scheme will be retained at the investigational site and will be available at the time of the site inspection to allow for verification of the treatment identity of each subject.

Masking codes should be broken only in emergency situations for reasons of subject safety. Whenever possible, the investigator or sub-investigator will consult with a member of the study team prior to breaking the mask. When the masking code is broken, the reason must be fully documented. At the initiation of the study, the study site will be instructed on the method for breaking the masking. The method will either be a manual or an electronic process.

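### Does Section 9.1.1 unmask site staff by giving them a treatment assignment along with the kit number?

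*Combined protocol and SAP*

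**What the plan says.** Section 9.1.1 sets out randomization as "computer generated, block treatment assignments in a 1:1 ratio stratified by investigational site", run through a web-based system (the ORS). The user is the study coordinator or another named designee. After the entries are made, "The site personnel will then be provided with a treatment assignment and Kit Number or container number when drug is being supplied" through that system. The same paragraph then describes the output that is filed: "The ORS system will provide a confirmation report containing the subject number or container number assigned". For further detail on using the system it points to a study-specific reference manual, which is not among the documents.

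Section 9.1.2 covers lost, damaged or used-up containers: "the Investigator will use the ORS, which will specify a new Kit Number to be dispensed to that subject".

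Section 9.2 states the masking: "The study subject, investigational staff, investigator, and sponsor personnel will be masked with respect to treatment group". It adds "A sealed copy of the randomization scheme will be retained at the investigational site", for use at inspection, and "Masking codes should be broken only in emergency situations for reasons of subject safety".

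Sections 10.1.1, 10.1.3 and 10.1.4 supply both products in masked outer packaging and keep site staff out of the room when the bottle is taken out or a dose is given.

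**The concern.** The sentence in 9.1.1 joins the assignment to the kit or container number with *and*, so the assignment reads as something additional to the coded number. Everywhere else in the protocol the term means the arm. Section 9.2 masks investigational staff without exception, and nobody who dispenses or uses the system is described as unmasked.

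If the system did display the arm, the mask would be broken for the coordinator at randomization. Site personnel review the dosing diaries (9.4), and the investigator or a designee documents deviations (9.5). Both feed the per-protocol population on which the primary equivalence analysis rests (13.2.1), and one of its conditions, freedom from deviations that matter to the evaluation, involves judgment. Because randomization is blocked within site, visible past assignments could also help predict later ones. In an equivalence trial with an active control, a break in masking would be a serious matter.

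**Working it through.** No figure in the plan bears on this point, so the check is a comparison of the text.

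**1. How the term is used.** *Treatment assignment(s)* occurs six times: once in the Synopsis, once in 7.1, twice in 9.1.1, once in 10.1.1 and once in 13.2.1 (1 + 1 + 2 + 1 + 1 = 6). Leaving out the disputed sentence, 6 − 1 = 5 remain, and all five refer to the arm.
- Three of them (Synopsis, 7.1 and the first use in 9.1.1) are near-identical statements about the 1:1 randomization list. They say nothing about what a site user sees. Counted as one, they leave three independent uses.
- Section 10.1.1 says that the container number links the medication to the assignment. On that arrangement the site needs only the number in order to dispense the right product.
- Section 13.2.1 allows further per-protocol criteria until the assignments are unmasked. Assignments therefore exist in masked form during the trial.

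The usage supports reading the term as the arm. It does not support the further step that the arm is displayed to the site.

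**2. What the site is told elsewhere.**

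| Step | Section | What is described |
|---|---|---|
| Randomization | 9.1.1 | Assignment, plus kit or container number |
| Confirmation report | 9.1.1 | Subject or container number |
| Replacement | 9.1.2 | New kit number |
| Labeling | 10.1.1 | Unique container number |
| Scheme held at site | 9.2 | Sealed, for inspection |
| Code-break | 9.2 | Emergencies only |

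Five of the six rows describe a coded or sealed process. The first is the only one that could be read otherwise, and it does not say that the assignment appears decoded.

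**3. Whether the literal reading is workable.** If the coordinator saw each arm at randomization, sealing the site's copy of the scheme and limiting code-breaks to emergencies would have little purpose, and 9.2 would be false from the first subject onward. The masked reading leaves every section consistent.

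**4. The route to the primary analysis.** Under 11.8, IOP is read by an MD or DO only, in duplicate, with a third reading if the two differ by more than 2 mmHg. The system user named first in 9.1.1 is the coordinator. The dosing limits for the per-protocol population are numerical (75% to 125% of planned doses, no gap of more than 3 consecutive days) and are verified from patient diaries. Section 9.5 has sites document and explain deviations; it does not give them the decision to exclude. A path to bias needs a decoded display, a user who acts on it, and an effect on exclusions or readings. The documents establish none of these.

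**The case for a change.** The strongest opposing case is that the surrounding text makes this sentence the outlier without reconciling it. A reader must override plain words to reach the intended meaning, in the very section that describes what the system returns. Masked packaging stops staff seeing a bottle but would not stop a screen naming an arm. The reference manual cannot be seen and so cannot be assumed to cure the conflict. System use is not kept apart from study tasks: 9.1.2 has the investigator using the system, the abbreviations section defines the investigator as the person responsible for assessments, and nothing bars a physician from being the designee. The mention of masked staff in 9.2 and 10.2 hints that unmasked staff may exist, but none are named.

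Much of this stands. The conflict in wording is real, packaging alone does not answer it, and 11.8 does not fully separate the IOP reader from the system user. The step from loose wording to an actual break of the mask does not stand. The masked reading rests on 9.2, the confirmation report, replacement by kit number, the sealed scheme and 13.2.1, so it does not depend on packaging or on the unseen manual. That manual cuts both ways: the documents cannot show what the screen displays, so they cannot show disclosure either. Prediction from blocks would also require the arms to be visible, and no block size is given from which to gauge it.

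**Conclusion.** This is a clerical slip in one phrase of 9.1.1, and no change to the plan follows. Read together, 9.1.1, 9.1.2, 9.2, 10.1.1 and 13.2.1 fix a masked procedure in which the site works from coded numbers, and a sponsor carrying out the whole plan would set the system up that way. Tidier wording would change neither what is done to subjects nor what the equivalence analysis concludes. The effect on the per-protocol population and on IOP cannot be sized from the documents, and none is shown. The conclusion assumes that the system is configured in line with 9.2. The documents support that assumption but cannot prove it; evidence that the arm was displayed to site users would be a matter of trial conduct and would need separate attention.
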